### **Acceptability - Satisfaction with the Mapping Exercise**

**Instructions: Please circle the number below that best describes your feelings about each statement.**

	Not at All	A Little Bit	Somewhat	Quite a Bit	Very Much
I liked the study mapping exercise.	0	1	2	3	4
The study mapping exercise was helpful to me.	0	1	2	3	4
I plan to continue to use what I learned.	0	1	2	3	4
The interventionist who led the mapping was competent.	0	1	2	3	4
The interventionist who led the mapping was sensitive.	0	1	2	3	4

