## 2.0 Objectives

We will conduct a one-arm pilot study of MAP among 24 colorectal cancer survivors within one year of completing active treatment. We will quantitatively and qualitatively describe recruitment and retention; intervention completion and acceptability; and variability and changes in proposed outcomes (i.e., measures of patient engagement, health outcomes) to guide future study planning. We will analyze collected maps, and describe factors and targets for intervention at multiple levels (individual/geographic/social/institutional).

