## 5.0 Study Outcomes and Study Measures

We will collect data at two different levels, the individual-level (feasibility, outcome measures), and multi-level contextual factors (MAP data). We will collect self-reported data either remotely or in person at baseline and two weeks after MAP.

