## **Mapping to Guide Self-Management in Cancer Survivors**

### Follow-Up Questionnaire

Study ID: \_\_\_\_\_  
Date: \_\_\_\_\_

Name of Facilitator: \_\_\_\_\_

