**Acceptability - Future Study Planning**

1. How important is it for people to have support in determining their own health-related goals following cancer treatment?

1	2	3	4	5	6
Not at all	A little bit	Somewhat	Moderately	Quite a bit	Very much

2. How interested would you be in meeting with someone to follow-up with you on the goals you chose during the study mapping exercise?

1	2	3	4	5	6
Not at all	A little bit	Somewhat	Moderately	Quite a bit	Very much

3. What person would you like to meet with to discuss those goals?

- a. A nurse
- b. Other healthcare provider
- c. A mental health provider
- d. A cancer survivor
- e. Any of the above people
- f. Other (please specify): \_\_\_\_\_

4. How often do you think it would be helpful to meet with someone to discuss your goals?

- a. Weekly
- b. Twice per month
- c. Monthly
- d. I do not think it would be helpful
- e. Other (please specify): \_\_\_\_\_

5. How would you like to meet with someone to discuss your goals?

- a. In person at the Cancer Center
- b. In person at my primary healthcare location
- c. On the telephone
- d. Over videoconferencing
- e. I would not like to meet with someone
- f. Other (please specify): \_\_\_\_\_

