**Index of Autonomous Functioning:**

Below is a collection of statements about your general experiences. Please indicate how true each statement is of your experiences on the whole. Remember that there are no right or wrong answers. Please answer according to what really reflects your experience rather than what you think your experience should be.

1. My decisions represent my most important values and feelings

1	2	3	4	5
not at all true	a bit true	somewhat true	mostly true	completely true

2. I strongly identify with the things that I do

1	2	3	4	5
not at all true	a bit true	somewhat true	mostly true	completely true

3. My actions are congruent with who I really am

1	2	3	4	5
not at all true	a bit true	somewhat true	mostly true	completely true

4. My whole self stands behind the important decisions I make

1	2	3	4	5
not at all true	a bit true	somewhat true	mostly true	completely true

5. My decisions are steadily informed by things I want or care about

[figure not shown]
1	2	3	4	5
not at all true	a bit true	somewhat true	mostly true	completely true

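### The follow-up questionnaire puts 20 planning, MAP-satisfaction, facility and facilitator-connection items ahead of the outcome scales and baseline does not, so a context effect on mean change cannot be excluded

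*Combined protocol and SAP*

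**What the plan says.** Section 2.0 sets out a "one-arm pilot study of MAP among 24 colorectal cancer survivors" and includes among its products the description of "variability and changes in proposed outcomes (i.e., measures of patient engagement, health outcomes) to guide future study planning". Section 5.0 states: "We will collect self-reported data either remotely or in person at baseline and two weeks after MAP". Section 9.2 summarizes the proximal outcomes, and change in the health outcomes, by means, standard deviations and 95% confidence intervals. It names variance as the main interest.

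Appendix F prints both forms. The follow-up form begins with the future-study planning block, which asks "How important is it for people to have support in determining their own health-related goals following cancer treatment" and "How interested would you be in meeting with someone to follow-up with you on the goals you chose during the study mapping exercise". Next come the mapping-satisfaction block, with statements such as "I plan to continue to use what I learned" and two ratings of the interventionist, then ratings of care at the medical center, then the HEAL scale about the person who led the mapping. Only after these come health behaviors, the autonomy scale (for example "My decisions are steadily informed by things I want or care about"), self-efficacy, perceived stress and PROMIS-29.

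Section 5.2.2.3 explains why HEAL is given at follow-up only. Nothing in the plan explains its position on the form, and order effects are not mentioned.

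**The concern.** A change score assumes that the two answers were given under comparable conditions. Here they are not. Before describing their behaviors, autonomy, confidence, stress and symptoms for the second time, participants have reflected on whether people need support in setting health goals, whether the mapping helped, whether they will go on using it, and how they felt about the facilitator. Some of this overlaps in content with the autonomy and self-efficacy items, and the question on how well emotional needs were addressed overlaps with the stress and mood items. Participants may answer later items so as to be consistent with earlier ones, or in the way they think the study hopes for.

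In a two-arm trial using one form, much of such an effect could cancel. Here there is one arm, participants know what they received, and every scale at issue is self-reported. No analysis of these data can separate a context effect from change after MAP. What is at stake is how the mean changes are read.

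**Working it through.** **1. Block order as printed in Appendix F**

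| Position | Baseline form | Follow-up form |
|---|---|---|
| Opening | Background questions | Future-study planning (5 items) |
| | | Mapping satisfaction (5 items: 3 on MAP, 2 on the interventionist) |
| | | Overall satisfaction with the medical center (3 items) |
| | | HEAL connection scale (7 items) |
| Then | Health behaviors | Health behaviors |
| Then | Autonomy | Autonomy |
| Then | Self-efficacy (two scales) | Self-efficacy (two scales) |
| Then | Perceived stress | Perceived stress |
| Then | PROMIS-29 | PROMIS-29 |
| Last | Financial toxicity | none |

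Items ahead of the outcome scales at follow-up with no baseline counterpart: 5 + 5 + 3 + 7 = 20. The outcome scales are in the same relative order on both forms, so the opening is the only difference in what precedes them. Health behaviors, themselves an outcome under Section 5.2.3.3, come directly after HEAL at follow-up. Autonomy and the later scales have the health-behavior block directly before them on both forms.

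**2. What the difference can touch**

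- Primary outcomes (Section 5.1): enrollment, participation and retention are counts of people. Block order does not enter them or the thresholds in Section 9.3.
- Variance of change (Section 9.2): a constant shift leaves the SD unchanged. If the shift varies between people, independently of true change, with SD equal to s times the SD of change, the SD is multiplied by √(1 + s²). For assumed s = 0.1, 0.2 and 0.3 this is 1.005, 1.020 and 1.044, an inflation of 0.5% to 4.4%.
- Mean change (Sections 2.0 and 9.2): a shift of b goes straight into the estimate.

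**3. Scale for the mean change, by assumption**

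The plan gives no figure to reproduce here, and no size for an order effect. I therefore took shifts b of 0.1 to 0.5 SD of change. Sample sizes are n = 24 (all enrolled) and n = 17 (0.70 × 24 = 16.8, the hypothesized retention).

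Half-width of the 95% interval for a mean change, in SD of change: t(0.975, n − 1)/√n.

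- n = 24: 2.069/4.899 = 0.42
- n = 17: 2.120/4.123 = 0.51

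The probability that the interval excludes zero when there is no true change comes from the noncentral t distribution with n − 1 degrees of freedom and noncentrality b√n (for b = 0.2 and n = 24: 0.2 × 4.899 = 0.98):

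| Assumed shift b | n = 24 | n = 17 |
|---|---|---|
| 0.1 SD | 0.08 | 0.07 |
| 0.2 SD | 0.16 | 0.12 |
| 0.3 SD | 0.29 | 0.21 |
| 0.5 SD | 0.65 | 0.49 |

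The nominal value is 0.05.

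**The case against.** The strongest reply has four parts.

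- **Adjacency.** The satisfaction items are not next to the autonomy and confidence items. Facility ratings, HEAL and the whole health-behavior section lie between, and a near-identical health-behavior section (only the recall window of the therapy question differs) precedes autonomy at baseline. This stands. It weakens the case for autonomy and the later scales, but does not equalize what came earlier, and it does not protect the health-behavior items themselves.
- **No evidence of an effect.** The opening items are ratings that allow negative answers. A dissatisfied participant, or one reminded of the burden of cancer, could shift the other way. This stands: the point is a risk, not a demonstrated bias. Appendix F is also only the printed order; the order of administration is not stated.
- **Limited consequence.** Feasibility is primary and variance is the main interest in the scales. Section 9.2 attaches change explicitly to the health outcomes only; the general reference to changes is in Section 2.0. Shifts of 0.1 to 0.3 SD are smaller than the interval half-width at n = 24. All of this stands. But changes are still a stated product, and sampling error does not remove a systematic shift.
- **Acceptability first.** Asking it early keeps it clear of carry-over from 29 symptom items. This is minor, because acceptability and HEAL have no baseline to be compared with.

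A reader might also infer that the "Name of Facilitator" line pushes the facilitator ratings upward. The documents do not support this. The same line heads the baseline form, participants already know who led their session, and nothing says that the facilitator sees the answers.

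**Conclusion.** The point holds as an avoidable difference between the two forms. On the printed order, 20 items about MAP, its facilitator, the medical center and future support precede the outcome scales at follow-up and none do at baseline. In a one-arm self-report study, a context or demand effect on mean change therefore cannot be excluded. It is plausibly favourable, but its existence, direction and size are unknown. The table above rests wholly on assumed shifts and shows only that a modest one could matter for how an interval is read.

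The feasibility endpoints are unaffected, and the SD of change would be inflated by at most 4.4% over the assumed range.

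Two stronger readings are tempting. One is that the change scores are known to be inflated by some percentage; any such figure would need both a shift and a true change to be chosen, and the documents give neither. The other is that an overstated effect will be carried into the efficacy trial. The plan says that feasibility rates (Section 9.3) and variance (Section 9.2) serve later planning, and nowhere commits to carrying an effect estimate forward. Nor do the documents show a problem with when the interview is held.

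**What to change.** In the Appendix F follow-up form, put health behaviors, autonomy, self-efficacy, stress and PROMIS-29 first, in baseline order. Move the three acceptability blocks and the HEAL scale to the end. Add a version flag for any follow-up forms already collected in the present order, so that changes can be reported with the form version known.

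The cost is a reordering of instruments in REDCap and on paper, plus one flag variable. No items, visits or staff are added, and no sample size or feasibility threshold changes.

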### **Acceptability - Overall Satisfaction**

**Instructions:** Please rate the services you received from our facility in general. Circle the number that best describes your experience.

	Very Poor	Poor	Fair	Good	Very Good
1. Degree to which healthcare providers addressed your emotional needs	1	2	3	4	5
2. Likelihood of your recommending this medical center to others	1	2	3	4	5
3. Overall rating of care given at the medical center	1	2	3	4	5

**HEAL - Patient-Provider Connection - Short Form:**

**Please respond to each item by marking one box per row.**

[figure not shown]
[figure not shown]
*Think of the person who worked with you to create a map of your experience with cancer during this study as the “healthcare provider”...*

	Not at all	A little bit	Somewhat	Quite a bit	Very much
I am satisfied with my healthcare provider.	 1	 2	 3	 4	 5
I trust my healthcare provider.	 1	 2	 3	 4	 5
My healthcare provider pays attention to my individual needs.	 1	 2	 3	 4	 5
My healthcare provider gives me support and encouragement.	 1	 2	 3	 4	 5
My healthcare provider respects me.	 1	 2	 3	 4	 5
I feel my healthcare provider understands me.	 1	 2	 3	 4	 5
	Never	Rarely	Sometimes	Often	Almost Always
My healthcare provider gives me enough information.	 1	 2	 3	 4	 5

**The next section will ask you some questions about your health behaviors.**

**Physical activities** are activities where you move and increase your heart rate above its resting rate, whether you do it for pleasure, work or transportation. The following questions ask about the amount and intensity of physical activity you usually do. The intensity of an activity is related to the amount of energy you use to do these activities.

**Examples of physical activity intensity levels:**

Light activities • your heart beats slightly faster than normal • you can talk and sing	 Walking Leisurely	 Stretching	 Vacuuming or Light Yard Work
Moderate activities • your heart beats faster than normal • you can talk but not sing	 Fast Walking	 Aerobics Class	 Strength Training
Vigorous activities • your heart rate increases a lot • you can't talk or your talking is broken up by large breaths	 Stair Machine	 Jogging or Running	 Tennis, Racquetball, Pickleball or Badminton

1. How physically active are you? (check one answer on each line)

	Does this accurately describe you?	
	Yes	No
a) I rarely or never do any physical activities.		
b) I do some light or moderate physical activities, but not every week.		
c) I do some light physical activity every week.		
d) I do moderate physical activities every week, but less than 30 minutes a day or 5 days a week.		
e) I do vigorous physical activities every week, but less than 20 minutes a day or 3 days a week.		
f) I do 30 minutes or more a day of moderate physical activities, 5 or more days a week.		
g) I do 20 minutes or more a day of vigorous physical activities, 3 or more days a week.		

**This section will ask you some questions about smoking. For the questions below, please try to select a single number.**

2. Have you smoked at least 100 cigarettes (5 packs=100 cigarettes) in your entire life?

- Yes
- No ➔ Go to Question B6.
- Don't know / Not sure ➔ Go to Question B6.

3. How many total years have you smoked (or did you smoke) cigarettes? Do not count any time you may have stayed off cigarettes.

\_\_\_\_\_ Years *If you smoked less than one year, write "1."*

4. On average when you have smoked, about how many cigarettes do you (or did you) smoke a day?

A pack usually has 20 cigarettes in it.

\_\_\_\_\_ Number of cigarettes per day

5. How long has it been since you last smoked a cigarette (even one or two puffs)?

*First check which one of the following choices applies to you. Then, if applicable, write a number on the line for how many days, weeks, months, or years it has been since your last cigarette.*

- I smoked a cigarette today (at least one puff).
- 1-7 days. ➔ Number of days since last cigarette: \_\_\_\_\_
- Less than 1 month. ➔ Number of weeks since last cigarette: \_\_\_\_\_
- Less than 1 year. ➔ Number of months since last cigarette: \_\_\_\_\_
- More than 1 year. ➔ Number of years since last cigarette: \_\_\_\_\_
- Don't know / Don't remember.

6. Which of the following phrases best characterizes you at this time? *(Please mark only one response.)*

- Normal, no complaints, no symptoms of disease
- Able to carry on normal activity, minor symptoms of disease
- Normal activity with effort, some symptoms of disease
- Care for self, unable to carry on normal activity or to do active work
- Require occasional assistance but able to care for most of personal needs
- Require considerable assistance for personal care
- Disabled, require special care and assistance
- Severely disabled, require continuous nursing care

7. How many times have you fallen in the last 6 months? \_\_\_\_\_ times

8. Have you used any of the following complementary and alternative therapies in the past 2 weeks?

	No	Yes
a. Special diets such as mostly vegetarian or low fat	 0	 1
b. Movement or physical therapies such as yoga, tai chi, massage, chiropractic, or electromagnetic therapy	 0	 1
c. High dose or mega vitamins (DO NOT include 1-a-day multivitamins), nutritional supplements, or herbal remedies	 0	 1
d. Homeopathy (small doses of drugs that in a healthy person would produce symptoms like those of the disease)	 0	 1
e. Mind/body therapies such as guided imagery/visualization, biofeedback, meditation, relaxation techniques, hypnosis/hypnotherapy, energy healing, therapeutic touch, or music therapy	 0	 1
f. Oriental therapies such as acupuncture, acupressure, Qigong, or Shiatsu	 0	 1
g. Self-help or support groups (either face-to-face or on the Internet)	 0	 1
h. Psychological therapy or counseling from a psychologist, psychiatrist, social worker, or any other mental health professional	 0	 1
i. Faith healing, laying on of hands, or any other spiritual or religious group experience	 0	 1
j. Personal prayer or personal spiritual healing	 0	 1
k. Other, please specify: _____	 0	 1

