### 5.2.3 Health outcomes

- 5.2.3.1 Psychological stress [Perceived Stress Scale, 4-item]
- 5.2.3.2 Symptoms [PROMIS Profile 29]
- 5.2.3.3 Health behaviors [items on tobacco use, physical activity, use of CHA]

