### 5.2.7 Clinical factors (cancer type, disease stage, recurrence status, type of treatment) factors will be abstracted from medical charts or self-reported.

## 6.0 Study-Related Activities

### 6.1 Overview of Study-Related Activities

	Pre-Study a	Baseline	MAP b Intervention c	Follow-up (2-week) d
Recruitment	X			
Informed consent	X			
Demographic and Clinical Factors		X		
Patient-Reported Outcomes		X		X
Intervention Completion			X	
Acceptability Ratings				X
Semi-structured Interview				X
Adverse event evaluation			X	X

a Pre-study requirements listed in table must be completed within 30 days prior to registration.

b MAP = Systems Support Mapping

c Intervention may be coordinated with future clinic visit; must be completed within 6 months of registration

d Follow-up visit to be completed 14 - 28 days after intervention

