### 9.2 Analysis of Secondary Objectives

To meet Objective 2.2.1, we will use descriptive statistics to summarize participant ratings of acceptability.

Descriptive statistics (means, standard deviations, 95% confidence intervals) will be used to summarize proximal outcomes and change in health outcomes by assessment measure to meet Objective 2.2.2. The primary interest will be in estimating the variance for use in planning future studies.

For Objective 2.2.3, the internal study team will work with external collaborators through an iterative process to facilitate a qualitative content analysis of the large quantity of textual MAP data. Specifically, we will first enter text data from the completed paper maps into a software program co-developed by [name] (external Senior Programmer, University of North Carolina-Chapel Hill Renaissance Computing Institute) and [name] (Consultant) using the *ssm* function to create a digital map. [name] will translate the text MAP data into lists that can be sorted by the study team (using the *sort* program). The *sort* program will allow us to group and code similar terms or concepts. Next, we will send our *sort* files back to [name] and he will use Python programming language to help aggregate the large amounts of textual

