**This section will ask you some questions about smoking. For the questions below, please try to select a single number.**

B2. Have you smoked at least 100 cigarettes (5 packs=100 cigarettes) in your entire life?

- Yes
- No ➔ Go to Question B6.
- Don't know / Not sure ➔ Go to Question B6.

B3. How many total years have you smoked (or did you smoke) cigarettes? Do not count any time you may have stayed off cigarettes.

\_\_\_\_\_ Years *If you smoked less than one year, write "1."*

B4. On average when you have smoked, about how many cigarettes do you (or did you) smoke a day?

A pack usually has 20 cigarettes in it.

\_\_\_\_\_ Number of cigarettes per day

B5. How long has it been since you last smoked a cigarette (even one or two puffs)?

*First check which one of the following choices applies to you. Then, if applicable, write a number on the line for how many days, weeks, months, or years it has been since your last cigarette.*

- I smoked a cigarette today (at least one puff).
- 1-7 days. ➔ Number of days since last cigarette: \_\_\_\_\_
- Less than 1 month. ➔ Number of weeks since last cigarette: \_\_\_\_\_
- Less than 1 year. ➔ Number of months since last cigarette: \_\_\_\_\_
- More than 1 year. ➔ Number of years since last cigarette: \_\_\_\_\_
- Don't know / Don't remember.

B6. Which of the following phrases best characterizes you at this time? *(Please mark only one response.)*

- Normal, no complaints, no symptoms of disease
- Able to carry on normal activity, minor symptoms of disease
- Normal activity with effort, some symptoms of disease
- Care for self, unable to carry on normal activity or to do active work
- Require occasional assistance but able to care for most of personal needs
- Require considerable assistance for personal care
- Disabled, require special care and assistance
- Severely disabled, require continuous nursing care

B7. How many times have you fallen in the last 6 months? \_\_\_\_\_ times

B8. **At any time** since you were first diagnosed with cancer, have you used any of the following complementary and alternative therapies?

	No	Yes	Have you used them in the past year?	
a. Special diets such as mostly vegetarian or low fat	0 	1 	→	0  No    1  Yes

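### Use of complementary health approaches is asked over a year or longer at baseline but over two weeks at follow-up, so its change and the variance of that change cannot be interpreted

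*Combined protocol and SAP*

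**What the plan says.** Section 5.2.3 names CHA use among the health outcomes: "Health behaviors [items on tobacco use, physical activity, use of CHA". Section 2.0 sets out to describe "variability and changes in proposed outcomes (i.e., measures of patient engagement, health outcomes) to guide future study planning". Section 9.2 says descriptive statistics will "summarize proximal outcomes and change in health outcomes by assessment measure", and adds: "The primary interest will be in estimating the variance for use in planning future studies". Under Objective 2.2.5, all quantitative analyses are repeated by rural-urban status.

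The CHA items in Appendix F differ between visits:

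- Baseline item B8 asks whether, at any time "since you were first diagnosed with cancer, have you used any of the following complementary and alternative therapies", and then, for each therapy reported, "Have you used them in the past year".
- Follow-up item 8 lists the same rows a to k but asks only "Have you used any of the following complementary and alternative therapies in the past 2 weeks".

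Section 6.1 fixes the timing in footnote d: "Follow-up visit to be completed 14 - 28 days after intervention".

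**The concern.** A change score needs the same quantity measured twice. Here the shortest baseline window is a year and the only follow-up window is two weeks. Someone who uses a therapy now and then, and does not alter that habit, will often answer Yes at baseline and No at follow-up. The plan's summary would record this as stopping.

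Three results could be misread: an apparent fall in CHA use after the mapping session (MAP), a real rise that is hidden, and a variance of change carried into the design of a later trial. A rural-urban comparison of CHA change inherits the problem, and Section 1.0 presents CHA use as higher in rural communities.

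The two-week follow-up window is sensible in itself: with a visit at least 14 days after the session, it looks back only over post-MAP time. What is missing is its baseline counterpart.

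**Working it through.** **Step 1: compare the items.** The plan states no rate, SD or power for CHA change, so there is no figure of its own to reproduce.

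| Health outcome | Baseline | Follow-up |
|---|---|---|
| Perceived stress | past 7 days | past 7 days |
| PROMIS-29 | 7 days where a window is given | same |
| Physical activity | usual activity, no recall window | same wording |
| Tobacco | lifetime use, time since last cigarette | same wording |
| CHA, rows a–k | since diagnosis; past year | past 2 weeks |

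Only CHA changes its window.

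**Step 2: direction.** With unchanged behaviour and accurate recall, a two-week window is not expected to capture more users than a year, so the expected net change is zero or negative. This holds in expectation, not in every sample. The windows are not nested in calendar time, so an occasional user with no past-year use at baseline can answer Yes at follow-up.

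**Step 3: size of the spurious fall.** Assume k independent therapies per user, each used on average once every d days as a Poisson process, with accurate recall. Then P(Yes in T days) = 1 − exp(−kT/d). Call this y for T = 365 and p for T = 14. The fall among past-year users is (y − p)/y. For k = 1 and d = 30, y = 1.000 and p = 1 − exp(−14/30) = 0.373, so the fall is 62.7 points.

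| Therapies (k) | daily | weekly | every 2 weeks | monthly | two-monthly |
|---|---|---|---|---|---|
| 1 | 0 | 14 | 37 | 63 | 79 |
| 2 (any CHA) | 0 | 2 | 14 | 39 | 63 |
| 3 (any CHA) | 0 | 0 | 5 | 25 | 50 |

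**Step 4: a hidden rise.** Take users of one therapy who move from monthly to weekly use. On matched two-week items the change is 0.865 − 0.373 = +0.492. On the planned items it is 0.865 − 1.000 = −0.135. A 49-point rise appears as a 14-point fall.

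**Step 5: variance of individual change, no true change.** Let P be the share of users, with windows independent given the rate.

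- Matched items: P·2p(1 − p).
- Planned items: P[y(1 − p) + (1 − y)p] − [P(p − y)]².

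For k = 1 and P = 0.30:

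- Weekly use (y = 1.000, p = 0.865): matched 0.30 × 2 × 0.865 × 0.135 = 0.070; planned 0.30 × 0.135 − (0.30 × 0.135)² = 0.039; ratio 0.55 (SD 0.197 against 0.265).
- Two-monthly use (y = 0.998, p = 0.208): matched 0.30 × 2 × 0.208 × 0.792 = 0.099; planned 0.181; ratio 1.83 (SD 0.426 against 0.314).

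Over P = 0.10 to 0.40, the one-therapy ratio of planned to matched variance is 0.55–0.57 (weekly), 0.67–0.76 (every two weeks), 1.0–1.3 (monthly) and 1.6–2.2 (two-monthly). For any CHA with two or three therapies and P = 0.30 to 0.40, it lies between 0.5 and 1.1. For daily use both variances are close to zero.

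**Step 6: check without the Poisson assumption.** Let q be the probability that a past-year user uses the therapy in a given two weeks. With no true change, the apparent mean change is −P(1 − q). For P from 0.30 to 0.40 and q from 0.9 to 0.25, it runs from −0.30 × 0.10 = −0.03 to −0.40 × 0.75 = −0.30. It vanishes only at q = 1.

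**The case against.** The wording mismatch is not in dispute. The case for giving it little weight has five parts.

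- **Small role.** CHA is one of three behaviours in one of three health-outcome lines. The sample size rests on feasibility rates, and Section 9.2 defines no CHA change score (any use, or row by row). Reporting each visit separately would be natural and is already sound. This limits the impact, but the plan as written still calls for change.
- **Sampling noise.** By a normal approximation, rough for binary data, a variance estimated from 24 people has a 95% interval of about 0.60 to 1.97 times the estimate (23 divided by the chi-square quantiles on 23 degrees of freedom). That is about the size of the artefact. The artefact is systematic, however, and the interval would not reveal it.
- **Assumed inputs.** Poisson use, a common rate, independent windows and the user shares are not in the documents. The list includes prayer, diets and supplements, which may be habitual, and for daily use the bias is negligible. The 30–40% in Section 1.0 does not refer to this 11-row list. At an assumed 80% users with two therapies used two-monthly, the variance ratio is (1 − 0.8 × 0.627)/(2 × 0.373) = 0.67, so overstatement may not arise for any-CHA use. The figures are therefore illustrative; the confounding itself follows from the wording.
- **Limits of new use.** A No since diagnosis followed by a Yes at follow-up is a real new start, but one since baseline, not necessarily since the session. With follow-up up to 28 days after the session, a brief trial that ended more than 14 days before the visit is missed, and resumption by earlier users is not counted.
- **Limits of the remedy.** The session may take place up to 6 months after registration (Section 6.1, footnote c), so even matched change in one arm is not specific to it. This argues for cautious interpretation, not for unmatched windows.

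The interviews and the maps give context on starting and stopping, but neither supplies a two-week baseline measure or a variance.

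**Conclusion.** The concern holds. Following Sections 2.0 and 9.2 as written gives a CHA change, a stopping rate and a change variance that cannot be separated from the switch of recall window. That conclusion needs no numerical assumption. Its size does: under the assumptions above, the spurious fall for one therapy ranges from nothing (daily use) to 79 points among past-year users (two-monthly use), and the planning variance can be too small or too large.

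The practical weight is modest, because this is one secondary descriptive outcome and its rural-urban comparison. The primary feasibility outcomes, the proportion reporting CHA at each visit and rural-urban comparisons within a visit are unaffected. New use since baseline also remains interpretable, within the limits noted.

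**What to change.** Add a Yes/No column for the past two weeks to the 11 rows of baseline item B8. Keep the since-diagnosis and past-year columns as descriptors. State in Section 9.2 that CHA change and its variance come only from the matched two-week items, and whether the score is any use or row by row.

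For participants enrolled without that column, report CHA use separately at each visit, plus new use among those with none since diagnosis, and give no net-change, change-variance or stopping summary. This fallback may matter in practice: Section 9.5 expected completion by April 2019, while reference 40 was accessed in June 2019, so enrolment may already be well advanced.

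The cost is 11 × 2 = 22 tick boxes, a revised Appendix F and a REDCap field update. The fallback needs no new data.
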